17.5. Boston Scientific Device Deficiencies

All device deficiencies (including but not limited to failures, malfunctions, use errors, product nonconformities, and inadequacy in the information supplied by the manufacturer) will be documented and reported to BSC.

Device deficiencies (including but not limited to failures, malfunctions, and product nonconformities) are not adverse events. However, an adverse event that results from a device failure or malfunction would be recorded as an adverse event on the appropriate eCRF.

Any Device Deficiency that might have led to a serious adverse event if a) suitable action had not been taken or b) intervention had not been made or c) if circumstances had been less fortunate is considered a reportable event.

17.6. Reporting to Regulatory Authorities / IRBs / ECs / Investigators

BSC is responsible for reporting adverse event information to all participating Principal Investigators and regulatory authorities, as applicable.

18. Informed Consent

Subject participation in this clinical study is voluntary. Informed Consent is required from each subject or his/her legally authorized representative. The Investigator is responsible for ensuring that Informed Consent is obtained prior to the use of any investigational devices, study-required procedures and/or testing, or data collection.

The obtaining and documentation of Informed Consent must be in accordance with the principles of the Declaration of Helsinki, ISO 14155:2011, any applicable national regulations, and local Ethics Committee and/or Regulatory authority body, as applicable. The ICF must be accepted by BSC or its delegate (e.g. CRO), and approved by the site's IRB/EC, or central IRB, if applicable.

Boston Scientific will provide a study-specific template of the ICF to investigators participating in this study. The ICF template may be modified to meet the requirements of the investigative site's IRB/EC. Any modification requires acceptance from BSC prior to use of the form. The ICF must be in a language understandable to the subject and if needed, BSC will assist the site in obtaining a written consent translation. Translated consent forms must also have IRB/EC approval prior to their use. Privacy language shall be included in the body of the form or as a separate form as applicable.

The process of obtaining Informed Consent shall at a minimum include the following steps, as well as any other steps required by applicable laws, rules, regulations and guidelines:

- be conducted by the Principal Investigator or designee authorized to conduct the process,
- include a description of all aspects of the clinical study that are relevant to the subject's decision to participate throughout the clinical study,
- avoid any coercion of or undue influence of subjects to participate,
- not waive or appear to waive subject's legal rights,
- use native language that is non-technical and understandable to the subject or his/her legal representative,
- provide ample time for the subject to consider participation and ask questions if necessary,
- ensure important new information is provided to new and existing subjects throughout the clinical study.

The ICF shall always be signed and personally dated by the subject or legal representative competent to sign the ICF under the applicable laws, rules, regulations and guidelines and by the investigator and/or an authorized designee responsible for conducting the informed consent process. If a legal representative signs, the subject shall be asked to provide informed consent for continued participation as soon as his/her medical condition allows. The original signed ICF will be retained by the site and a copy of the signed and dated document and any other written information must be given to the person signing the form.

Failure to obtain subject consent will be reported by BSC to the applicable regulatory body according to their requirements (e.g., FDA requirement is within 5 working days of learning

of such an event). Any violations of the informed consent process must be reported as deviations to the sponsor and local regulatory authorities (e.g. IRB/EC), as appropriate.

If new information becomes available that can significantly affect a subject's future health and medical care, that information shall be provided to the affected subject(s) in written form via a revised ICF or, in some situations, enrolled subjects may be requested to sign and date an addendum to the ICF. In addition to new significant information during the course of a study, other situations may necessitate revision of the ICF, such as if there are amendments to the applicable laws, protocol, a change in Principal Investigator, administrative changes, or following annual review by the IRB/EC. The new version of the ICF must be approved by the IRB/EC. Acceptance by Boston Scientific is required if changes to the revised ICF are requested by the site's IRB/EC. The IRB/EC will determine the subject population to be reconsented.

19. Suspension or Termination

19.1 Premature Termination of the Study

Boston Scientific Corporation reserves the right to terminate the study at any stage but intends to exercise this right only for valid scientific or administrative reasons and reasons related to protection of subjects. Investigators, associated IRBs/ECs, and regulatory authorities, as applicable, will be notified in writing in the event of study termination.

19.1.1 Criteria for Premature Termination of the Study

Possible reasons for premature study termination include, but are not limited to, the following.

- The occurrence of unanticipated adverse device effects that present a significant or unreasonable risk to subjects enrolled in the study.
- An enrollment rate far below expectation that prejudices the conclusion of the study.
- A decision on the part of Boston Scientific to suspend or discontinue development of the device.

19.2 Termination of Study Participation by the Investigator or Withdrawal of IRB/EC Approval

Any investigator, or IRB/ EC in the Non-Complex Biliary Stones DSC vs ERC RCT may discontinue participation in the study or withdrawal approval of the study, respectively, with suitable written notice to Boston Scientific. Investigators, associated IRBs/ECs, and regulatory authorities, as applicable, will be notified in writing in the event of these occurrences.

19.3 Requirements for Documentation and Subject Follow-up

In the event of premature study termination a written statement as to why the premature termination has occurred will be provided to all participating sites by Boston Scientific. The

IRB/EC and regulatory authorities, as applicable, will be notified. Detailed information on how enrolled subjects will be managed thereafter will be provided.

In the event an IRB or EC terminates participation in the study, participating investigators, associated IRBs/ECs, and regulatory authorities, as applicable, will be notified in writing. Detailed information on how enrolled subjects will be managed thereafter will be provided by Boston Scientific.

In the event a Principal Investigator terminates participation in the study, study responsibility will be transferred to another investigator, if possible. In the event there are no opportunities to transfer Principal Investigator responsibility; detailed information on how enrolled subjects will be managed thereafter will be provided by Boston Scientific.

The Principal Investigator or his/her designee must return all study-related documents and investigational product to Boston Scientific, unless this action would jeopardize the rights, safety, or welfare of the subjects.

19.4 Criteria for Suspending/Terminating a Study Site

Boston Scientific Corporation reserves the right to stop the inclusion of subjects at a study site at any time after the study initiation visit if no subjects have been enrolled for a period beyond 6 months after site initiation, or if the site has multiple or severe protocol violations/noncompliance without justification and/or fails to follow remedial actions.

In the event of termination of site participation, all study devices and testing equipment, as applicable, will be returned to BSC unless this action would jeopardize the rights, safety or well-being of the subjects. The IRB/EC and regulatory authorities, as applicable, will be notified. All subjects enrolled in the study at the site will continue to be followed for 30 days after index procedure per the study protocol. The Principal Investigator at the site must make provision for these follow-up visits unless BSC notifies the investigational site otherwise.

20. Publication Policy

BSC requires disclosure of its involvement as a sponsor or financial supporter in any publication or presentation relating to a BSC study or its results. BSC will submit study results for publication (regardless of study outcome) following the conclusion or termination of the study. Boston Scientific Corporation adheres to the Contributorship Criteria set forth in the Uniform Requirements of the International Committee of Medical Journal Editors (ICMJE; http://www.icmje.org). In order to ensure the public disclosure of study results in a timely manner, while maintaining an unbiased presentation of study outcomes, BSC personnel may assist authors and investigators in publication preparation provided the following guidelines are followed.

- All authorship and contributorship requirements as described above must be followed.
- BSC involvement in the publication preparation and the BSC Publication Policy should be discussed with the Coordinating Principal Investigator(s) and/or Executive/Steering Committee at the onset of the project.

• The First and Senior authors are the primary drivers of decisions regarding publication content, review, approval, and submission.

21. Bibliography

22.1. Abbreviations

Abbreviations are shown in Table 22.1-1.

Abbreviation/Acronym	Term
ADE	Adverse Device Effect
AE	Adverse Event
BD	Bile Duct
BSC	Boston Scientific Corporation
CBD	Common Bile Duct
СР	Chronic Pancreatitis
CRF	Case Report Form
CRO	Contract Resource Organization
CSEMS	Covered Self-Expanding Metal Stent
СТ	Computed Tomography
DFU	Directions for Use
DSC	Direct Solitary Cholangioscopy
eCRF	Electronic Case Report Form
EC	Ethics Committee
EDC	Electronic Data Capture
EHL	Electro-Hydraulic Lithotripsy
EPS	Endoscopic Pancreatic Sphincterotomy
ERC	Endoscopic Retrograde Cholangiography
ERCP	Endoscopic Retrograde
	Cholangiopancreatography
FDA	Food and Drug Administration
GCP	Good Clinical Practices
ICF	Informed Consent Form
ICH	International Conference on Harmonization

Table 22.1-1: Abbreviations

Abbreviation/Acronym	Term
INR	International Normalized Ratio
IRB	Institutional Review Board
ISO	International Standards Organization
ITT	Intent-to-Treat
LL	Laser Lithotripsy
LFT	Liver Function Test
MRCP	Magnetic Resonance Cholangiopancreatography
PD	Pancreatic Duct
PI	Principal Investigator
PP	Per Protocol
PT	Prothrombin Time
PTT	Partial Thromboplastin Time
SADE	Serious Adverse Device Effect
SAE	Serious Adverse Event

Table 22.1-1: Abbreviations

22.2. Definitions

Terms are defined in Table 22.2-1.

Term	Definition
Acute Pancreatitis	Abdominal pain and a serum concentration of pancreatic enzymes (lipase(required, amylase (optional)) three or more times the upper limit of normal, that required more than one night of hospitalization
Acute Cholecystitis	No suggestive clinical or radiographic signs of acute cholecystitis before the procedure and if emergency cholecystectomy is subsequently required
Perforation	Retroperitoneal or bowel-wall perforation documented by any radiographic technique or direc visual evidence.
Wound Infection	Requiring intervention otherwise considered as minor complication
Cholangitis	Elevation in termperature more than 38°C, thought to have a biliary cause, without concomitant evidence of acute cholecystitis, requiring intervention.
Hemorrhage	Bleeding after the index procedure requiring transfusion of ≥ 4 units of packed cells within a 24-hour period, or leading to relaparotomy/intervention

Term	n Definition	
(Emergency)	Any (other) reason following either preoperative biliary drainage or another surgical procedure	
Pneumonia	Pulmonary infection with radiological confirmation and requiring antibiotic treatment	
Mortality	In-hospital death, due to protocol complications or any cause, including progression of disease, within the study period.	
Abbreviations are define	ad in Table 22.1.1	

Table 22.2-1: Definitions

Abbreviations are defined in Table 22.1-1.

Probability of stones based on ASGE criteria are defined in Table 22.3-1.

Table 22.23-2: Predictors of Choledocholithiasis			
Predictors of choledocholithiasis			
Very strong			
CBD stone on transabdominal US			
Clinical ascending cholangitis			
Bilirubin >4 mg/dL			
Strong Dilated CBD on US (>6 mm with gallbladder in situ) Bilirubin level 1.8mg/dL – 4 mg/dL			
Moderate			
Abnormal liver biochemical test other than bilirubin			
Age older than 55 y			
Clinical gallstone pancreatitis			
Assigning a likelihood of choledocholithiasis based on clinical predictors			
Presence of any very strong predictor High			

E7131 Confidential	Non-Complex Biliary Stones DSC vs ERC RCT Template 90702637 Rev/Ver AH	
	Page 51 of 51	
Presence of both strong predictors	High	
No predictors present	Low	
All other patients	Intermediate	

Abbreviations are defined in Table 22.1-1.

1 PROTOCOL SUMMARY

[figure not shown]
Г

E7131 – Non-Complex Biliary Stones DSC vs ERC RCT		
Study Objective	To prospectively compare non-complex biliary stone clearance using fluoroscopy/radiation-free direct solitary cholangioscopy (DSC) utilizing the SpyGlass TM system with non-complex biliary stone clearance using standard endoscopic retrograde cholangiography (ERC).	
Indication(s) for Use	 SpyGlassTM DS Digital Controller is intended to provide illumination and receive, process, and output images from the SpyScopeTM DS Access and Delivery Catheter for diagnostic and therapeutic applications during endoscopic procedures in the pancreatico-biliary system including the hepatic ducts. SpyScopeTM DS Access and Delivery Catheter is intended to provide direct visualization and to guide both optical and accessory devices for diagnostic and therapeutic applications during endoscopic procedures in the pancreatico-biliary system including the hepatic ducts. The following devices will be available upon commercialization: SpyScopeTM DS II Access and Delivery Catheter is intended to provide direct visualization and to guide both optical and accessory devices for diagnostic and therapeutic applications: SpyScopeTM DS II Access and Delivery Catheter is intended to provide direct visualization and to guide both optical and accessory devices for diagnostic and therapeutic applications during endoscopic procedures in the pancreatico-biliary system including the hepatic ducts. SpyScopeTM DS II Access and Delivery Catheter is intended to provide direct visualization and to guide both optical and accessory devices for diagnostic and therapeutic applications during endoscopic procedures in the pancreatico-biliary system including the hepatic ducts. SpyGlassTM Retrieval Basket is indicated for the endoscopic removal of stones, stone fragments, or foreign bodies in the pancreaticobiliary system. SpyGlassTM Retrieval Snare is indicated for the endoscopic retrieval of foreign bodies in the 	
Device	SpyGlass™ Digital System	
Study Design	 Prospective Consecutive cases Multi-center Randomized 1:1 ratio: Group A (ERC arm): Clearance of bile duct stones using standard-of-practice ERCP techniques 	

E/131	 Non-Complex Biliary Stones DSC vs ERC RCT Group B (DSC arm): Clearance of bile duct stones using DSC techniques Block-randomization by site Non-inferiority hypothesis Validation of stone clearance by ERC in DSC arm and by DSC in ERC arm. 	
Number of Subjects	 250 subjects An additional 5 Roll-in cases. Each participating endoscopist at each of the participating centers must perform up to 5 Roll-in cases. These roll-in cases will not count towards enrollment ceiling of 250 cases. Procedures to be conducted only by the Principal Investigator. Sub-Investigators will be authorized to do study procedures only on an exception basis. Such exception may be granted by the Sponsor in consultation with the Principal Investigator of the site and Lead Principal Investigator to the study. 	
Number of Sites	Up to 15 global sites	
Primary Endpoint	Complete stone clearance by extraction of bile duct stones from the common bile duct (CBD) into duodenum as determined by fluoroscopy free cholangioscopy in the DSC arm and by cholangiography in the ERC arm.	
Secondary Endpoints	1. Evaluation of all serious adverse events (SAEs) including all deaths (related and unrelated), severity, onset, time to resolution related to the DSC devices and/or procedure and/or the ERC procedure through 30 days post procedure.	
	2. Radiation exposure to the patient (total fluoroscopy time, total radiation dose, Dose Area Product (DAP), effective dose), from duodenoscope in to completion of stone clearance, not including the validation DSC procedure in ERC arm and ERC procedure in DSC arm.	
	 Duration of procedure defined as time from duodenoscope in to completion of stone clearance, not including the validation DSC procedure in ERC arm and ERC procedure in DSC arm. 	
Follow-up Schedule	 Telephone follow-up during the following post-procedure intervals: 24 hours 7 days 	

E7131 – Non-Complex Biliary Stones DSC vs ERC RCT			
	• 30 days		
Study duration	Approximately 2 years		
Inclusion Criteria	 18 years or older Abdominal pain consistent with choledocholithiasis (procedure possible within 72 hours of onset of symptoms and imaging suggesting choledocholithiasis, contingent on persistent abdominal pain) Abnormal LFTs 		
	 4. Non-complex biliary stone disease, defined as 5 or fewer stones in the common bile or common hepatic duct with largest stone no larger than 10 mm in size. If stones not seen on imaging (US, CT) the bile duct diameter should be ≤12 mm* 		
	* Given the poor sensitivity (approximately 20%) for biliary stones of CT and US, the diameter of the dilated CBD is used as a surrogate for largest stone diameter		
	5. Availability of non-invasive imaging to determine the diameter of the bile duct and number and size of bile duct stones if visible on imaging		
	a. If probability of stones is high per investigator assessment based on ASGE criteria, any standard of practice imaging modality (eg. abdominal US) is acceptable.		
	 b. If the probability of stones is either intermediate or low per investigator assessment based on ASGE criteria, MRCP or EUS imaging is required to confirm presence of stones. 		
	6. Willing and able to comply with the study procedures and provide written informed consent to participate in the study		
Exclusion Criteria	 Potentially vulnerable subjects, including but not limited to pregnant women and subjects in whom an endoscopic procedure is contraindicated 		
	 Location of the stones in intrahepatic ducts, cystic duct or proximal to strictures 		
	3. Bile duct stricture noted distal to stone on MRCP, which would make extraction without lithotripsy impossible		

E7131	l – Non-Complex Biliary Stones DSC vs ERC RCT		
E7151	 4. Ongoing cholangitis at time of randomization, manifested by fever with tachycardia and hypotension or evidence of pus at the ampulla 		
	5. Patients with prior biliary sphincterotomy		
	6. Patients with Primary Sclerosing Cholangitis (PSC)		
	7. Acute pancreatitis, defined as abdominal pain and serum concentration of pancreatic enzymes [lipase (required), amylase (optional)] three or more times the upper limit of normal		
	8. Surgically altered gastro-duodenal luminal anatomy other than prior Billroth I reconstruction, as these would be anticipated to lead to more complicated procedures		
	9. Coagulopathy or ongoing need for anti-coagulation		
Statistics	• Preliminary DSC-guided stone clearance rate was established in a Pilot study ¹ and found to be comparable to that of ERC-guided stone clearance.		
	 Eight relevant peer-reviewed publications²⁻⁹ reporting on ERC-guided biliary stone clearance rates, representing 2721 patients were analyzed. A meta-analysis was conducted of the biliary stone clearance rates, yielding a point estimate of 90% with a 95% CI of [85%, 94%] (see Forest plot below). Based on the two observations provided above, we hypothesize that the DSC-guided stone clearance rate is non-inferior to that of the ERC-guided stone clearance rate. We assume a DSC-guided and ERC-guided stone clearance rate of 90% and use a 10% non-inferiority margin for the sample size calculation provided below. The 10% non-inferiority margin is based on the fact that in the references used for the meta-analysis²⁻⁹ stone clearance rates above 80% eliminate the lowest performing publications. 		
	Test Method: An exact test will be used to test the one-sided hypothesis of non- inferiority of the DSC-guided vs ERC-guided stone clearance rates		
	Sample Size: To detect non-inferiority of the clearance rate in DSC arm compared to the ERC arm with 80% power and one-sided alpha=0.05, a sample of 250 total is needed.		

2 INTRODUCTION

This statistical plan addresses the planned analyses for the study on Non-Complex Biliary Stones DSC vs ERC based on the protocol dated February 16th 2018, Version D2. Specified analyses may be used for scientific presentation and/or manuscripts and may not all be provided to Competent Authorities.

3 ENDPOINT ANALYSIS

3.1 Primary/Secondary Safety/Efficacy/Effectiveness Endpoint

The primary endpoint is complete stone clearance by extraction of bile duct stones from the common bile duct (CBD) into duodenum as determined by fluoroscopy free cholangioscopy in the DSC arm and by cholangiography in the ERC arm.

Preliminary DSC-guided stone clearance rate was established in a pilot study¹ and found to be comparable to that of ERC-guided stone clearance. Eight relevant peer reviewed publications²⁻⁹ reporting on ERC-guided biliary stone clearance rates representing 2721 patients were analyzed. A meta-analysis was conducted of the biliary stone clearance rates, yielding a point estimate of 90% with a 95% CI of [85%, 94%].

3.1.1 Hypotheses

We hypothesize that the DSC-guided stone clearance rate is non-inferior to that of the ERC-guided stone clearance rate. We assume a DSC-guided and ERC-guided stone clearance rate of 90% with a 10% non-inferiority margin. The following hypothesis will be tested:

H₀: P_{DSC} minus $P_{ERC} \le -\Delta$ (Inferior) H₁: P_{DSC} minus $P_{ERC} > -\Delta$ (Non-inferior)

where P_{DSC} and P_{ERC} are the stone clearance rates for the DSC arm (test) and the ERC arm (control), respectively, and (Δ delta) is the non-inferiority absolute margin.

Form/Template 90702621 Rev/Ver AE < Non-Complex Biliary Stones RCT, document 92232577, Rev/Ver AA > Page 9 of 13

3.1.2 Sample Size

The sample size was estimated based on the following assumptions:

- Expected stone clearance rate of 90% in DSC-guided and ERC-guided group
- Non-inferiority margin: 10%
- Alpha (1-sided): 0.05
- Power: 80%

With the above assumptions, a sample of 250 patients (125 in each arm) is needed to detect the non-inferiority of the clearance rate in the DSC arm compared to the ERC arm. This sample size was calculated using StatXact 9[®].

3.1.3 Statistical Methods

An exact test will be used to test the non-inferiority hypothesis of the DSC-guided vs. ERC-guided stone clearance rates.

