8.5. Randomization

Randomization is to occur only after verification of all inclusion/exclusion criteria. Once the patient has signed the IRB/EC-approved study ICF and has met all general inclusion and none of the exclusion criteria, the patient will be eligible for randomization.

Randomization will be stratified by clinical site. Within each site, eligible subjects will be randomized in a 1:1 ratio to receive each treatment method. This study is not blinded.

For back-up randomization, sites will be instructed to randomize patients via back-up envelopes only in cases of unsuccessful access to the online database system. Envelopes are sequentially numbered sealed opaque envelopes containing randomized treatments.

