9.1.3. Statistical Methods

An exact test will be used to test the non-inferiority hypothesis of the DSC-guided vs. ERC-guided stone clearance rates.

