5.10 Changes to Planned Analyses

Any changes to the planned statistical analyses made prior to performing the analyses will be documented in an amended Statistical Analysis Plan approved prior to performing the analyses. Form/Template 90702621 Rev/Ver AE < Non-Complex Biliary Stones RCT, document 92232577, Rev/Ver AA > Page 11 of 13

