7 PROGRAMMING CONSIDERATIONS

7.1 Statistical Software

All statistical analyses will be done using The SAS System software, version 8 or higher (Copyright © 2000 SAS Institute Inc., SAS Campus Drive, Cary, North Carolina 27513, USA. All rights reserved). StatXact9® software may be used for the primary endpoint analysis, as SAS does not provide exact non-inferiority test at the time of writing this SAP.

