7.3 Rules and Definitions

- Binary event rates (proportions) will be reported on a per-patient basis.
- The last follow-up date will be the latest of the following dates for each patient: date of an adverse event, procedure date, follow-up visit date, and device event date.
- Serious Adverse Event will be defined as an adverse event that:
 - Led to death
 - Led to a serious deterioration in the health of the subject that either resulted in:
 - a life-threatening illness or injury, or
 - a permanent impairment of a body structure or a body function, or
 - in-patient hospitalization or prolonged hospitalization (of an existing hospitalization), or
 - medical or surgical intervention to prevent life-threatening illness or injury or permanent impairment to a body structure or a body function
 - Led to fetal distress, fetal death, or a congenital abnormality or birth defect.
- When calculating rates of adverse events, missing and partial dates will be handled as follows:

Partial Date Description	Action Taken
Entire onset date is missing	The procedure date will be used for the
	onset date.

Form/Template 90702621 Rev/Ver AE < Non-Complex Biliary Stones RCT, document 92232577, Rev/Ver AA > Page 12 of 13

Partial Date Description	Action Taken
The month and the day of the month are	January 1 will be used for the month and
missing but the year is available	day of the onset date. However, if the
	imputed date falls before the procedure
	date, then the procedure date will be used
	for the onset date.
Day is missing, but the month and year are	The 1 st will be used as the day of the onset
available	date. However, if the imputed date falls
	before the procedure date, then the
	procedure date will be used for the onset
	date.

Form/Template 90702621 Rev/Ver AE < Non-Complex Biliary Stones RCT, document 92232577, Rev/Ver AA > Page 13 of 13

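### Does an unnamed exact test leave the non-inferiority verdict open?

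*SAP*

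**What the plan says.** SAP 3.1.3: "An exact test will be used to test the non-inferiority hypothesis of the DSC-guided vs. ERC-guided stone clearance rates". Protocol 9.1.3 has the same sentence ("An exact test will be used to test the non-inferiority hypothesis"), and the synopsis adds that the test is one-sided.

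SAP 3.1.2 fixes the rest: 90% clearance in both arms, a 10-point margin, one-sided alpha 0.05, 80% power and 125 patients per arm. On its origin it says "This sample size was calculated using StatXact 9". SAP 7.1 adds that StatXact 9 "software may be used for the primary endpoint analysis, as SAS does not provide exact non-inferiority test". SAP 5.10 gives the route for later changes: "Any changes to the planned statistical analyses made prior to performing the analyses will be documented in an amended Statistical Analysis Plan".

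Neither document specifies a confidence limit for the difference. The margin has one stated reason, in SAP section 1 and the Protocol synopsis: among the meta-analysed publications, "stone clearance rates above 80% eliminate the lowest performing publications".

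**The concern.** An exact test of a non-zero difference between two proportions is a family of tests. The analyst must choose the statistic that orders the outcomes and decide how to deal with the unknown ERC rate. Two members of the family can both hold 5% and still pass and fail the same table. Protocol 8.5 states "This study is not blinded", so a choice made late could be made with the counts in view. The lower confidence limit for the difference also depends on which test is inverted, and readers need that limit to judge the result against a stricter margin.

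The margin sentence adds to the unease. Its 80% floor excludes a single publication, which by its title concerns stones over 2 cm, while this trial enrols stones of at most 10 mm.

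**Working it through.** **Inputs** (SAP 3.1.1 and 3.1.2): n = 125 per arm; H0: P_DSC − P_ERC ≤ −0.10; one-sided 5%; planning rates 90% and 90%.

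**1. The plan's own figure.** The normal approximation gives (1.645 + 0.842)² × 2 × 0.9 × 0.1 / 0.10² = 111.3, so 112 per arm or 224 in total. That is not the plan's number, as expected for an exact test. I then enumerated all 126 × 126 outcomes and maximised the tail probability over the boundary P_DSC = P_ERC − 0.10. With the score statistic (variance from the constrained maximum-likelihood rates), 122 per arm gives 79.5% power, 123 gives 80.2% and 125 gives 81.7%. The planned 250 therefore reproduces.

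**2. Three exact tests at 125 per arm**, each maximised over the full range of the ERC rate:

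| Statistic | Maximum type I error | Power at 90/90 |
|---|---|---|
| Score | 4.95% | 81.7% |
| Unpooled Z | 3.10% | 69.8% |
| Raw difference | 4.95% | 45.8% |

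The raw-difference test passes only if DSC has at least one more clearance than ERC. It demands numerical superiority, so it is not a credible choice for a non-inferiority question, and I set it aside when judging size.

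**3. Score against unpooled Z.** Every outcome that passes with the unpooled Z also passes with the score test. The verdicts therefore differ with probability 81.7 − 69.8 = 11.9% at 90/90, always with the score test passing. The raw-difference region also lies inside the score region. Picking the most favourable of the three after seeing the counts is thus the same as using the score test, with type I error at most 4.95%.

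**4. A worked table.** DSC 110/125 (88.0%), ERC 113/125 (90.4%), observed difference −2.4 points.

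- Score: constrained rates 0.828 and 0.928; standard error √[(0.828 × 0.172 + 0.928 × 0.072)/125] = 0.0409; z = (−0.024 + 0.10)/0.0409 = 1.86 against a critical value of 1.663; p = 0.034; lower limit −9.25 points. Passes.
- Unpooled Z: standard error √[(0.88 × 0.12 + 0.904 × 0.096)/125] = 0.0392; z = 0.076/0.0392 = 1.94 against 2.140; p = 0.060; lower limit −10.34 points. Fails.

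The 0.060 arises at a true ERC rate of 100%. All 125 ERC patients then clear, and a z of 1.94 or more needs at least 118 DSC clearances; P(Binomial(125, 0.90) ≥ 118) = 0.060. At ERC rates of 85%, 90%, 95% and 98% the same tail probability is 0.028, 0.030, 0.033 and 0.038. The failure comes from a corner that 113/125 already rules out.

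**5. The margin sentence.** From the forest plot in the Protocol synopsis, 162/216 = 75.0% is the only rate below 80%; the next lowest is 57/69 = 82.6%. A random-effects model on the logit scale reproduces the pooled 90% [85%, 94%]; without the over-2-cm publication it gives 91.5% [86.8%, 94.6%].

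**The case for a change.** The best case for a change is that the score test has to be inferred. A reader must back-calculate 250 to find it, and SAP 7.1 makes StatXact optional. Score and unpooled Z are both standard statistics, they disagree in about one trial in eight at the planning rates, and the disagreements fall near the margin, where the verdict matters most. One sentence would settle both the test and the matching limit, at no cost in patients or data.

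The factual part stands: the statistic is not named, no limit is specified, and the 11.9% is right for full-range maximisation. What does not stand is the inference that the verdict is unprotected. The disagreement runs one way only, so the freedom cannot produce an unwarranted pass among these tests. Departing from the score test would only cost the sponsor power. The gap also narrows when the range of the unknown rate is restricted by a confidence interval; I give no figure because it depends on the interval used. The claim that only one exact test reaches 80% holds for the three compared, not for all exact tests, since other score-based versions also reach it.

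The criticism of the margin sentence is fair as far as it goes. It leaves 10 points and 250 patients untouched and offers no better reason in its place.

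**Conclusion.** No change to the plan is needed. Followed as written, it gives a valid one-sided 5% test whichever of the compared versions is run. The version that reproduces the planned 250 patients has 81.7% power and a maximum type I error of 4.95%, so the plan's 80% and 5% both hold. An analyst filling the gap would use the test behind the sample size and report the lower limit from inverting it. That is ordinary practice, and SAP 5.10 provides a route if the sponsor wishes to write it down.

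The residual exposure is one of power: 69.8% instead of 81.7% if the unpooled Z were used with full-range maximisation. The margin's stated reason is a separate minor weakness that changes no result.

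This rests on 125 evaluable patients per arm, true rates of 90% in both arms, and the inference, which the documents do not state, that the score version was used for the sample size.
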